2 SAMPLE SIZE DETERMINATION

Part B will enroll approximately 23 participants. The sample size is designed to provide an estimate of the true response rate. If 5 responders are observed out of 23 treated participants, the observed response rate is 22% (90% CI: 9%, 40%), with the lower bound of the exact 90% CI exceeding 8%, which is the historical standard of care response rate estimated from a pooled analysis of 8 randomized studies in ITP participants.

28-Nov-2022 Version number: 1

3 ANALYSIS POPULATIONS

The following populations for analyses are defined:

Table 3 - Populations for analyses

Population	Description All participants who signed the ICF.		
Screened			
Enrolled	All participants from screened population who have been allocated to an intervention regardless of whether the intervention was received or not.		
Exposed	All screened participants who have taken study intervention, regardless of the amount administrated.		
Intent-to-treat (ITT)	All enrolled participants.		
Safety	All enrolled participants who have taken investigational medical product (IMP), regardless of the amount administered.		
Pharmacokinetic (PK)	All enrolled participants from the safety population who have at least one post- baseline PK result.		

4 STATISTICAL ANALYSES

This SAP is based on protocol Version 15, dated 19 March 2021.

4.1 GENERAL CONSIDERATIONS

In general, continuous data will be summarized using the number of observations available, mean, standard deviation, median, (Q1, Q3 if applicable), minimum, and maximum. Categorical and ordinal data will be summarized using the count and percentage of participants.

The baseline value is defined as the last available value before the first dose of investigational medicinal product (IMP). For participants enrolled, however not treated, the baseline value is defined as the last available value before enrollment.

Baseline of platelet count is defined as the average of three platelet counts: two qualified screening platelet counts collected in eCRF and Week 1 (study day 1) platelet count.

Observation period

The observation period will be divided into 3 segments:

- The **pre-treatment period** is defined as the period up to date of first investigational medicinal product (IMP) administration.
- The **on-treatment period** is defined as the period from the first dose of IMP to the last dose of IMP + 1. The on-treatment period includes the main on-treatment period and the long-term extension (LTE) on-treatment period.
 - If the subject did not enter LTE, the **main on-treatment period** is defined as from the date of first dose of IMP to the date of the last dose of IMP + 1.
 - If the subject entered LTE, the **main on-treatment period** is defined as from the date of first dose of IMP to the date before the first dose of IMP during LTE. Date of first dose during LTE is based on the date of dosing reported on LTE Cycle 1 Day 1 (C1D1 LTE) in Study Drug Administration eCRF.
 - LTE on-treatment period is defined as from the date of first dose of IMP during LTE to the last dose of IMP + 1.
- The **post-treatment period** is defined as the period from the end of the on-treatment period.

The **treatment-emergent period** is any time after the first administration of rilzabrutinib. Treatment-emergent (TE) period includes both on-treatment period and post-treatment period. That is, **main treatment-emergent period** includes main on-treatment period and post-treatment period for those did not enter LTE; **LTE treatment-emergent period** includes LTE on-treatment period and post-treatment period.

Property of the Sanofi group - strictly confidential

4.2 PARTICIPANT DISPOSITIONS

The number (%) of participants included in each of the analysis populations listed in Table 3 will be summarized.

Screen failures are defined as participants who consent to participate in the study but are not subsequently enrolled. The number (%) of screen failures and reasons for screen failures will be provided in the screened population.

The number (%) of participants in the following categories will be provided:

- Enrolled participants
- Enrolled but not exposed participants
- Enrolled and exposed participants
- Participants who completed the main study period
 - Participants who completed 12 weeks of treatment
 - Participants who completed 24 weeks of treatment
- Participants who did not complete main 24-week study period and main reason for permanent IMP discontinuation
- Participants who entered LTE
 - Ongoing in LTE
 - Discontinued from LTE and main reason for discontinuation
- Status at the last contact (alive, dead).

In addition, the number (%) of participants screened, screened-failed, enrolled, entered LTE, with early study discontinuation will be provided by country and site.

Protocol deviations

Major protocol deviations will be tabulated by the deviation categories based on enrolled population.

Participants impacted by Covid-19 will be summarized upon data availability, such as discontinuation due to Covid-19, protocol deviation due to Covid-19, and visit(s) impacted by Covid-19 etc. as collected in eCRF.

Page 68

4.3 PRIMARY ENDPOINT(S) ANALYSIS

4.3.1 Definition of endpoint(s)

Proportion of participants able to achieve platelet counts $\geq 50,000/\mu$ L on at least 8 out of the last 12 weeks [Week 14 (Day 92) to Week 25 (Day 169)] of the 24-week treatment period without the use of rescue medication after 10 weeks of active treatment.

4.3.2 Main analytical approach

The responder of the primary endpoint must have met ALL of the following criteria:

 Platelet counts ≥ 50,000/µL for at least 8 out of the last 12 weeks [Week 14 (Day 92) to Week 25 (Day 169)] during the 24-week treatment period (or equivalently the ontreatment period for efficacy).

The on-treatment period for efficacy is defined as the period from the date of the 1st IMP administration

- up to 1 day after the last IMP administration for participants who did not enter LTE, or
- Week 25 (Day 169) visit for participants who entered LTE.

The on-treatment period for efficacy will be used for all efficacy analyses related to platelet counts.

And,

- Not rescued after 10 weeks of treatment. "Rescued after 10 weeks of treatment" for efficacy analysis is defined as from Week 11 (Day 71) to the day prior to the last date of IMP administration for those do not enter LTE or the visit date of Week 25/C1D1_LTE (Day 169) for those entered LTE.
- Not discontinued before Week 25 due to related TEAE (per investigator's assessment), lack of response, or need to rescue medication as recorded in eCRF, i.e., participants who discontinue before Week 25 and the discontinuation reasons are treatment related adverse event (AE), lack of response, or need of rescue medication will be considered as non-responders.

The response rate will be summarized for ITT population along with the 95% exact Clopper-Pearson Confidence Interval (CI).

Platelet counts and the change from baseline will be summarized by visit. The time course of platelet count will be described graphically, and the following plots will also be provided:

- Individual platelet count profile: line plot of platelet count by visit for each participant
- Spaghetti plot platelet count by participant in each study period (i.e., main and LTE)
- Median platelet count/change from baseline by visit in each study period

Property of the Sanofi group - strictly confidential

28-Nov-2022 Version number: 1

An unscheduled platelet count will be allocated to a scheduled visit if it is within the visit window of the scheduled visit where a platelet count is not available (see Section 5.3).

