### 4.12.2 Allowed Part B

- All patients may receive, but are not required to be taking, concomitant corticosteroids. The dose should be fixed (±10%) for at least 2 weeks before Day 1 and remain unchanged throughout the active treatment period of the study unless rescue criteria are triggered or patient experiences corticosteroid-associated adverse events that require a reduction of steroid dose. Patients who continue in the LTE period will be able to taper corticosteroid dose if platelet counts are ≥100,000/μL. Tapering would follow the following guidelines with 2 weekly platelet counts between tapers:
  - 10 mg/day every one to two weeks from an initial dose >40 mg of prednisone or equivalent per day
  - 5 mg/day every one to two weeks at prednisone doses ≤40 to >20 mg or equivalent per day
  - 2.5 mg/day every one to two weeks at prednisone doses ≤20 to >10 mg or equivalent per day
  - 1 mg/day every one to two weeks at prednisone doses ≤10 to >5 mg or equivalent per day

- 0.5 mg/day every one to two weeks at prednisone doses ≤5 mg or equivalent per day down to zero. This can be achieved by alternating daily doses (eg, 5 mg on Day one and 4 mg on day two)
  - Dose of corticosteroid can be up-titrated if platelet counts fall below  $50,000/\mu L$  on two consecutive measurements
- All patients may receive, but are not required to be taking, eltrombopag, romiplostim, or avatrombopag. The dose should be fixed for at least 2 weeks before Day 1 and remain constant (10% variation from Day 1 daily dose is allowed) throughout the study unless there are safety concerns related to those drugs.
- Patients may receive another treatment for ITP (one form of IVIg, high-dose steroids, platelet infusion, or anti-D immunoglobulin infusion) if there is a significant safety event requiring "rescue" from a deterioration in the patient's platelet count that in the opinion of the Investigator puts the patient at significant risk of a safety event. Patients who receive rescue therapy will be allowed to continue if none of the stopping rules apply (Section 4.6) and the Investigator agrees to continue treating the patient with rilzabrutinib.

•					

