4.4.2 Main analytical approach

All secondary endpoints will be assessed during the 24-week treatment period unless otherwise specified. The number (percent) will be summarized for the ITT population along with the 95% exact Clopper-Pearson CI for the categorical endpoints.

• Number of weeks with platelet count ≥50,000/μL OR ≥30,000/μL and doubling the baseline in the absence of rescue therapy (platelet counts will be censored for 4 weeks after the use of rescue medication, if given)

Property of the Sanofi group - strictly confidential

To qualify for the criteria specified in the endpoint at a given week, the participant must have met ALL the following criteria,

- Platelet count ≥50,000/μL OR ≥30,000/μL and doubling the baseline at a given week during the 24-week treatment period from Week 2 (Day 8) to Week 25 (Day 169),
- Not rescued within the 4 weeks prior to the elevated platelet count at the given week, that is, if the participants received rescue medication during the 24-week treatment, platelet counts will be censored from the date when the rescue medication is initiated up to 4 weeks after the use of rescue medication, i.e., any weeks that fall into this period will be considered as not qualifying for the criteria specified.

95% CI of mean using t-distribution will be provided.

• Number of weeks with platelet counts ≥30,000/µL and doubling from baseline over the 24-week treatment period: this endpoint will be derived similarly as the secondary endpoint above.

95% CI of mean using t-distribution will be provided.

• Proportion of all treated participants able to achieve two or more consecutive platelet counts, separated by at least 5 days of $\geq 50,000/\mu L$ AND an increase of platelet count of $\geq 20,000/\mu L$ from baseline without use of rescue medication in the 4 weeks prior to the latest elevated platelet count

To qualify for a responder, the participant must have met the following criteria

[figure not shown]
- \geq 2 consecutive platelet counts \geq 50,000/ μ L, separated by at least 5 days, and
- An increase of platelet count of ≥20,000/μL from baseline, and
- Not rescued within the 4 weeks prior to the latest elevated platelet count
- Proportion of participants receiving rescue medications

The number and proportion of participants receiving rescue medications will be tabulated respectively

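### Part B primary endpoint: a platelet count within 4 weeks of rescue can still qualify if rescue fell on Days 64–70 (Days 61–70 with an early Week 14 visit), unlike in the platelet secondary endpoints

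*SAP*

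**What the plan says.** SAP Part B 4.3.1 asks for counts of at least 50,000/µL on at least 8 of the last 12 weeks "of the 24-week treatment period without the use of rescue medication after 10 weeks of active treatment". Section 4.3.2 turns this into dates:

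- The scored counts are the 12 weekly ones from Week 14 (Day 92) to Week 25 (Day 169).
- Rescue after 10 weeks "for efficacy analysis is defined as from Week 11 (Day 71) to the day prior to the last date of IMP administration" for those who do not enter the long-term extension (LTE), and runs to the Week 25 visit for those who do. Rescue in that period makes a non-responder.
- Stopping before Week 25 for a related adverse event, lack of response or need of rescue also makes a non-responder.
- Nothing discounts an individual count because it follows rescue.

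SAP Part B 4.4.2 handles the platelet secondary endpoints differently. For the two weeks-of-response endpoints, "platelet counts will be censored from the date when the rescue medication is initiated up to 4 weeks after the use of rescue medication", and "any weeks that fall into this period will be considered as not qualifying for the criteria specified". For the endpoint based on two consecutive counts, the criterion is "Not rescued within the 4 weeks prior to the latest elevated platelet count".

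A rescued Part B participant can go on to be scored. Protocol 4.12.2 says: "Patients who receive rescue therapy will be allowed to continue if none of the stopping rules apply", provided the investigator agrees. SAP 4.3.3 plans no sensitivity analysis of the primary endpoint.

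**The concern.** The rescue treatments listed in Protocol 4.12.2 (IVIg, high-dose steroids, platelet infusion, anti-D) are given because the platelet count has deteriorated. A count taken soon afterwards may reflect the rescue and not rilzabrutinib, and 4.4.2 guards against this with a 4-week rule. The primary endpoint, which is the measure of durable response, has only the interval between Day 71 and Day 92, which is 21 days. The same Week 14 count can therefore be excluded as rescue-affected in the secondary tables and still supply one of the 8 weeks for a primary response. With about 23 participants, a single borderline classification shows in the response rate.

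**Working it through.** **Inputs**

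- Target day of Week n = 1 + 7 × (n − 1), window ±3 days (SAP 5.3, Table 6). Week 14 = 1 + 7 × 13 = Day 92, window Days 89–95. Week 15 = 1 + 7 × 14 = Day 99, window Days 96–102.
- Last rescue day that does not count against the primary: Day 70 (4.3.2).
- Post-rescue period: 4 weeks = 28 days (4.4.2), taken here as including day 28 and running from the last day of rescue use.

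**Which rescue dates are exposed**

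1. Week 14 visit on its target day: 92 − 70 = 22 days, and 92 − 28 = Day 64. Rescue on Days 64–70 (70 − 64 + 1 = 7 days) is not counted, yet the Week 14 count lies within 28 days of it.
2. Week 14 visit on Day 89: 89 − 70 = 19 days, and 89 − 28 = Day 61. The slice widens to Days 61–70 (10 days). A late visit on Day 95 narrows it: 95 − 28 = Day 67, so Days 67–70.
3. Week 15 on its target day: 99 − 70 = 29 days, outside the period. Only an early visit is exposed: 96 − 28 = Day 68 and 70 + 28 = Day 98, so rescue on Days 68–70 with a Week 15 count on Days 96–98.

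The reach is one scored count of 12 at target days, and two at most.

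**Supplementary analyses in 4.3.4**

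- Two-thirds analysis: uses the same 12 weeks and the same Day 71 rule, so it is exposed in the same way.
- Primary endpoint met or LTE entered: exposed through its primary component. The result changes only for a participant who did not enter the LTE, because one who did is counted anyway.
- Biweekly analysis (Weeks 15, 17, 19, 21, 23, 25): exposed only through the early Week 15 visit in step 3.

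**Size**

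One participant is 1/23 = 4.3 percentage points. The exact (Clopper-Pearson) limits for x of n are the α/2 quantile of Beta(x, n − x + 1) and the 1 − α/2 quantile of Beta(x + 1, n − x). The first row reproduces the benchmark in SAP Part B section 2, which is 22% (90% CI 9% to 40%).

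| Responders | Rate | Exact 90% CI | Exact 95% CI |
|---|---|---|---|
| 5/23 | 21.7% | 9.0% to 40.4% | 7.5% to 43.7% |
| 4/23 | 17.4% | 6.2% to 35.5% | 5.0% to 38.8% |

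**How often the Week 14 count decides**

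The documents give no weekly response probability, so this is an assumption. If the other 11 weekly counts are independent, each with chance p of being at least 50,000/µL, a high Week 14 count is decisive when exactly 7 of the 11 are high: C(11,7) × p^7 × (1 − p)^4. This is 2% at p = 0.3, 16% at 0.5, 24% at 0.6, 22% at 0.7 and 11% at 0.8. Independence is a simplification, since counts within a person are likely to be correlated.

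**The case against.** The strongest reply is that the 10-week limit is the protocol's own. Protocol 3.4.2 words the endpoint that way, 10 completed weeks end on Day 70 (10 × 7), and Day 71 follows. No passage sets 4 weeks as the carry-over period for the primary endpoint, and a 12-week responder endpoint may have a different rescue rule from a count of weeks. This stands to the extent that no rule written for the primary is broken. It does not explain why a shorter period suits the durability measure, and the documents give no reason.

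Four stronger readings are tempting, and the documents do not support them:

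- **The primary is generally looser on rescue.** One rescue from Day 71 makes the participant a non-responder outright, whereas the weeks-of-response secondaries lose only the weeks up to 4 weeks after its use. The primary is looser only within the slice above.
- **Day 71 is a slip for Day 64.** The Week 10 visit falls on Day 64 (1 + 7 × 9), exactly 28 days before Day 92, so a reader might infer an offset between visit label and elapsed time. Nothing in the documents says so.
- **All supplementary analyses share the gap.** At target days the biweekly analysis does not.
- **One participant decides whether Part B beats the 8% historical rate.** The fall in the 90% lower bound from 9.0% to 6.2% comes from a planning illustration, not a decision rule. The planned interval in 4.3.2 is 95%, and for 5/23 it already starts at 7.5%.

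Timing is also a fair objection. This is an open-label study, and the SAP was approved when all enrolled participants had concluded 24 weeks of treatment. Altering the primary definition now needs care, which governs the form of the remedy.

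**Conclusion.** The inconsistency is real and narrow. For rescue on Days 64–70 at target visit days, or Days 61–70 with an early Week 14 visit, the primary endpoint can credit a count that 4.4.2 would not let qualify for the platelet secondaries. The classification changes only if a participant was rescued in that slice, stayed on treatment, had a high count at Week 14 (or an early Week 15) and had just enough qualifying counts overall. The documents do not say how many participants were rescued then, and it may be none. It is worth correcting because the endpoint is meant to show durability and nothing else planned removes the affected count. It is not a reason to distrust the primary analysis as a whole.

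A separate conflict bears on this. Protocol 3.4.2 and SAP 4.3.1 limit the rescue condition to the time after 10 weeks, while the protocol synopsis and section 10.2 set no time limit. Under the wording without a limit, the gap in the primary endpoint would close by itself. These passages must be reconciled.

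**What to change.** Add a sentence to SAP Part B 4.3.2, carried through to 4.3.4: any Week 14–25 platelet count within 4 weeks after rescue is not qualifying, whenever the rescue was given. Use the flag already derived for 4.4.2 and keep the rule that rescue from Day 71 makes a non-responder. In the two-thirds analysis, leave a flagged count in the denominator as not qualifying and do not set it to missing; this matches how 4.4.2 treats such weeks.

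If results are already known, leave the primary definition alone and report this as a labelled sensitivity analysis under 4.3.3, with the number of participants rescued on Days 61–70. Protocol 2.2 already refers to preliminary Part B results, so this is the likelier route. If that number is zero, one line settles the matter.

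The programming cost is small. The downside is that the response rate could fall by a participant. Changing the definition itself would also mean departing from the wording of Protocol 3.4.2, so it should be done together with the reconciliation of the rescue wording.

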4.3.3 Sensitivity analysis

NA.

4.3.4 Supplementary analysis

The following supplementary analyses will be performed to further evaluate the durable platelet response during the 24-week treatment period. The proportion will be summarized along with the 95% exact Clopper-Pearson CI for the ITT population.

- Proportion of participants who have met the primary endpoint (Section 4.3.2) or entered LTE,
- Number/proportion of participants able to achieve platelet counts ≥ 50,000/µL for ≥two-thirds of at least 8 non-missing weekly scheduled platelet measurements during the last 12 weeks of the 24-week treatment period without the use of rescue medication after 10 weeks of active treatment, provided that at least 2 non-missing weekly scheduled platelet measurements are at or above 50,000/µL during the last 6 weeks of the 24-week treatment period.

To qualify for a responder, a participant must have met the following criteria

- At least 8 non-missing weekly scheduled platelet measurements during the last 12 weeks of the 24-week treatment period, and
- Platelet counts $\geq 50,000/\mu L$ for \geq two-thirds of 8 non-missing weekly assessments, and
- at least 2 platelet counts ≥50,000/μL occurred during the last 6 weeks of the 24-week treatment period, and
- Not rescued after 10 weeks of treatment (see Section 4.3.2 for details), and
- Not discontinued before Week 25 due to related TEAE (per investigator's assessment), lack of response, or need of rescue medication as recorded in eCRF.

The last 6 weeks are Week 20 (Day 134) to Week 25 (Day 169).

• Number/proportion of participants able to achieve platelet counts ≥50,000/μL on at least 4 out of the last 6 biweekly platelet counts during the 24-week treatment period without the use of rescue medication after 10 weeks of active treatment.

To qualify for a responder, a participant must have met the following criteria

- Platelet counts $\geq 50,000/\mu L$ for at least 4 out of the last 6 biweekly platelet counts during the 24-week treatment period, and
- Not rescued after 10 weeks of treatment (see Section 4.3.2 for details), and

28-Nov-2022 Version number: 1

- Not discontinued before Week 25 due to related TEAE (per investigator's assessment), lack of response, or need of rescue medication as recorded in eCRF.

The last 6 biweekly counts will be at Weeks 15, 17, 19, 21, 23, and 25.

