# Long Term Extension (LTE)

After completing the active treatment period, patients who respond to rilzabrutinib will be allowed to enter the LTE. A platelet response is defined as platelet count  $\geq 50,000/\mu L$ , or  $\geq 30,000/\mu L$  and doubling of baseline at  $\geq 50\%$  of the visits during the last 8 weeks of the active treatment period (a minimum of 4 visits per the Schedule of Assessments) will be required. Baseline should be calculated as an average of platelet counts used for enrollment per Inclusion Criterion #4.

A patient may continue in the LTE until:

a) The patient is no longer responding as described in the table below:

[figure not shown]
Time in the LTE	'No response' platelet counts defined as <30,000/μL or <20,000/μL above baseline based on:		
C1_LTE through C6_LTE	4 consecutive weekly visits		
C7_LTE through C12_LTE	2 consecutive monthly visits		
QX_LTE	I quarterly visit  In this case, a second platelet count has to be obtained in one month to confirm lack of response		

In the LTE, patients will be monitored weekly for the first 6 months, monthly for an additional 6 months, then once every 3 months with the assessments as outlined in the LTE Schedule of Assessments Appendix 5 and Appendix 6.

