4.4 SECONDARY ENDPOINT(S) ANALYSIS

4.4.1 Definition of endpoint(s)

The secondary endpoints are defined below:

- Number of weeks with platelet count ≥50,000/μL OR ≥30,000/μL and doubling the baseline in the absence of rescue therapy (platelet counts will be censored for 4 weeks after the use of rescue medication, if given)
- Proportion of all treated participants able to achieve two or more consecutive platelet counts, separated by at least 5 days of ≥50,000/μL AND an increase of platelet count of ≥20,000/μL from baseline without use of rescue medication in the 4 weeks prior to the latest elevated platelet count
- Number of weeks with platelet counts ≥30,000/µL and doubling from baseline over the 24-week treatment period (platelet counts will be censored for 4 weeks after the use of rescue medication, if given)
- Proportion of participants receiving rescue medication
- Change from baseline in ITP Bleeding Scale (IBLS)

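### The first Part B supplementary durable-response analysis counts every long-term extension entrant without the rescue condition that the primary endpoint and the other two supplementary analyses apply

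*SAP*

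**What the plan says.** SAP Part B Section 4.3.4 gives three supplementary analyses intended to "further evaluate the durable platelet response during the 24-week treatment period". The first is the "Proportion of participants who have met the primary endpoint (Section 4.3.2) or entered LTE". It lists no further conditions. The other two each spell out responder criteria, and both include this one: "Not rescued after 10 weeks of treatment (see Section 4.3.2 for details), and". The primary endpoint in Section 4.3.2 carries the same requirement, "Not rescued after 10 weeks of treatment", counted from Week 11 (Day 71).

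Who enters the LTE is set by the protocol (Section 4.2 for Part B): "After completing the active treatment period, patients who respond to rilzabrutinib will be allowed to enter the LTE". The response definition that follows is platelet counts alone: at least 50,000/µL, or at least 30,000/µL with doubling of baseline, at half or more "of the visits during the last 8 weeks of the active treatment period (a minimum of 4 visits per the Schedule of Assessments"). It neither excludes rescued patients nor sets aside counts taken after rescue.

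In Part A, rescue leads to discontinuation (protocol Section 4.5.1). In Part B it need not: "Patients who receive rescue therapy will be allowed to continue if none of the stopping rules apply" and the investigator agrees (Section 4.12.2).

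The SAP's platelet-based secondary endpoints also deal with rescue. For the two that count weeks with response, "platelet counts will be censored for 4 weeks after the use of rescue medication, if given" (Section 4.4.1). The endpoint based on two consecutive counts excludes rescue in the preceding 4 weeks.

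**The concern.** The three supplementary analyses share one purpose, yet only the first can credit a participant whose counts were supported by rescue medication. A participant rescued after Day 70 fails the primary endpoint and the other two supplementary analyses. If the same participant reaches the LTE platelet threshold and enters, the first analysis counts a durable response.

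The result is a proportion with an exact 95% confidence interval in the ITT population, shown next to the primary rate. A reader would take it as a broader measure of durable response to rilzabrutinib. With about 23 participants, one or two such cases would visibly move it, and nothing in the proportion would show why.

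**Working it through.** **Inputs**
- N = 23, with the illustration of 5 responders, 22% (90% CI 9% to 40%), and a historical rate of 8% (SAP Part B Section 2).
- 95% exact Clopper-Pearson interval for the supplementary proportions (Section 4.3.4).
- Weekly visits at target Day 1 + 7(n − 1) (SAP Part B Appendix 3, Table 6).
- LTE entry: at least 50% of visits in the last 8 weeks, minimum 4 (protocol Section 4.2).
- Rescue failure from Day 71 (Section 4.3.2); 4-week (28-day) post-rescue window (Sections 4.4.1 and 4.4.2).

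**Step 1: reproduce the plan's figure.** 5/23 = 21.7%. The exact 90% interval is 8.98% to 40.39%, which matches the stated 22% (9%, 40%).

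**Step 2: the last 8 visits.** The SAP sets the last 12 weeks as Week 14 (Day 92) to Week 25 (Day 169) and the last 6 as Week 20 (Day 134) to Week 25. By the same convention the last 8 are Weeks 18 to 25: Days 120, 127, 134, 141, 148, 155, 162 and 169.

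**Step 3: visits inside one post-rescue window.** For rescue on day r, count the visits d with r < d ≤ r + 28.
- r = 113: Days 120, 127, 134 and 141, so 4 visits (113 + 28 = 141).
- r = 147: Days 148, 155, 162 and 169, so 4 visits.
- Every r from 113 to 147 gives 4. Counting a visit on the rescue day itself, or a course of several days, can only add to this.

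4/8 = 50%, which is the LTE minimum. If the effect lasts 21 days, one rescue covers at most 3 of these visits; if 14 days, at most 2. Qualifying would then need repeat rescue or other raised counts.

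**Step 4: the same participant under each rule.** Take a rescue on Day 113, qualifying counts at the four visits in the window, and none elsewhere.
- Primary endpoint: non-responder, because rescue falls after Day 70 and 4 counts fall short of 8 of 12.
- Second and third supplementary analyses: non-responder, because of the rescue condition.
- First supplementary analysis: responder, if the participant enters the LTE.

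**Step 5: size.** Each such participant adds 1/23 = 4.3 percentage points. The documents do not give the number, so take the 5/23 illustration plus k such entrants, assuming no other LTE entrants beyond the primary responders:

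| k | Proportion | Exact 95% CI |
|---|---|---|
| 0 | 5/23 = 21.7% | 7.5% to 43.7% |
| 1 | 6/23 = 26.1% | 10.2% to 48.4% |
| 2 | 7/23 = 30.4% | 13.2% to 52.9% |
| 3 | 8/23 = 34.8% | 16.4% to 57.3% |

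One such participant takes the 95% lower bound from below 8% to above it. On the 90% interval that the SAP uses for its own comparison, 5/23 already clears 8% (8.98%).

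**The case against.** The case on the other side is substantial.

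- **Discontinuation is largely covered.** A reader might infer that the LTE branch also drops the requirement of no discontinuation before Week 25 for a related adverse event, lack of response or need of rescue. It does not in substance: entry comes only after the active treatment period is completed. The rescue condition is what is missing.
- **A composite at or above the primary rate is not itself a defect.** A union with the primary endpoint must equal or exceed it. The threshold of 30,000/µL with doubling is the protocol's own LTE definition and appears in a listed secondary endpoint. Both are legitimate choices for a looser supplementary analysis.
- **Not every feature of the LTE branch inflates.** Participants who qualify but decline the LTE are not counted unless they meet the primary endpoint, which lowers the proportion. Only the missing rescue condition acts upward alone.
- **The 4-week window is an analysis convention.** No passage says that one rescue raises counts for 4 weeks. This limits the single-rescue case but not the gap: any LTE entrant rescued after Day 70 is counted, whatever produced the counts.
- **Rescue may be handled elsewhere.** The protocol describes LTE entrants as responders to rilzabrutinib, which shows intent. The Part B individual stopping rules (Section 4.6.1) appear partly unreadable and could remove some rescued patients. But Section 4.12.2 still expressly allows continuation, and the readable entry definition has no rescue clause.
- **The protocol's exploratory 4-of-the-last-8-weeks endpoint** (Section 10.4) also states no rescue condition, and its SAP derivation is not readable. The inconsistency claimed here is with the primary, secondary and other supplementary platelet rules only.
- **The information will exist.** Rescue use, LTE entry and individual platelet profiles are all planned outputs, so rescued entrants could be traced. The proportion and its interval would still include them.

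**Conclusion.** The gap in the definition is real and its consequence is limited. As written, the first supplementary analysis can count as durable a participant whom the primary endpoint fails for rescue after Day 70. Each one adds 4.3 points. On the 5/23 illustration, one moves the 95% lower bound from 7.5% to 10.2%, past the 8% historical rate.

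This rests on the readable text of the LTE and rescue provisions. The scenario in which one rescue supplies every qualifying count also assumes an effect of about 4 weeks. The number of such participants is not in the documents and may be zero.

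Two stronger readings are tempting and unsupported. One is that the Part B efficacy conclusion is compromised: the primary endpoint has its own rescue rule, and no decision rule attaches to this proportion. The other is that rescued patients have in fact inflated the result: the documents show only that the rule permits it. The point is a cheap improvement to a supplementary analysis.

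**What to change.** In SAP Part B Section 4.3.4, reword the first bullet so that a participant counts if the primary endpoint is met, or if the participant entered the LTE and was not rescued after 10 weeks of treatment as Section 4.3.2 defines it. Report the number of LTE entrants rescued after 10 weeks separately.

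No extra exclusion of counts within 4 weeks of rescue is needed. Under this condition the last permitted rescue day is Day 70, and 70 + 28 = Day 98, before the first of the last 8 visits at Day 120. For a course given over several days, the 28 days run from its last day.

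The analysis still measures LTE entry. The LTE entry rule and its platelet threshold stay as they are. The change uses rescue dates and entry status already collected and costs one line of SAP text; the proportion may be slightly lower. If the analysis has already been run, give the rate without rescued entrants beside it and label it as an added analysis.
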